9.2 Informed Consent

For candidates interested in the study, a copy of the consent form will be mailed to the candidates to look over for at least 1 day before obtaining consent.

The informed consent process is to be completed at the screening visit. Prior to conducting any study-related procedures, written informed consent must be obtained from the subject. The nature, scope and possible consequences, including risks and benefits, of the study will be explained to the subject by the PI or designee in accordance with the regulations and guidelines in the Statement of Compliance.

The recruiting investigators/coordinators will be trained to discuss the study with the potential participants only limited to the informed consent document, including that the potential participant will continue the receive the same medical care regardless whether he/she decide to participate in the study. The potential participant selection process will be independent of the potential participants' diabetes care provider.

To avoid the financial participant support/study compensation being an undue influence, we will not share the financial participant support information during screening telephone calls unless the subject asks or after they have verbally agreed that they would like to participate. We also will not disclose details in compensation before completion of consenting process.

As much time as needed will be used to allow adequate time to exchange information and questions during the recruitment. The subjects and the investigators should not feel rushed for the recruitment process.

9.3 Study Entrance Criteria

At Screening, each subject will be assessed for eligibility against the inclusion/exclusion criteria. Subjects who do not meet the study entrance criteria will not be allowed to enroll and participate in the study. Further recruitment criteria is to be applied prior to the randomization and study drug intervention. The reason(s) for ineligibility will be documented in the subject research chart.

9.4 Demographics and Medical History

Subject information including gender, age, date of birth, race, ethnicity, diagnosis of type 1 diabetes, and other relevant past medical history will be collected during the screening period and recorded in the appropriate CRF.

9.5 Laboratory Variables

Comprehensive Metabolic Panel, HbA1c and pregnancy test will be performed as indicated on the Study Calendar. Comprehensive Metabolic Panel and HbA1c Analyses of laboratory samples will be performed with ARUP Laboratories ([name]) protocol and supplies or at ARUP Laboratories. Pregnancy test will be performed with Immunostics Inc. ([name]) protocol and material.

9.5.1 Comprehensive Metabolic Panel

Phlebotomy will be conducted for the Comprehensive Metabolic Panel analysis, including Albumin, Alkaline Phosphatase, Aspartate Aminotransferase, Alanine Aminotransferase, Total Bilirubin, Calcium, Carbon Dioxide, Creatinine, Chloride, Glucose, Potassium, Protein, Sodium and Urea Nitrogen.

9.5.2 HbA1c

Phlebotomy will be conducted for the HbA1c assessment.

9.5.3 Pregnancy Testing

Urine collection will be conducted for Qualitative Beta-human chorionic gonadotropin assessment.

9.5.4 Specimen Collection, Preparation, Storage and Shipping

Specimen collection, preparation, storage and shipping will be conducted as the standard based on ARUP laboratory and Immunostics Inc. protocol.

9.6 Physical Examination

Physical examination, including respiratory, cardiovascular, abdominal and others as indicated based on medical history, will be conducted at the screening visit. For the follow-up visits, focused physical examination will be conducted at discretion of PI/sub-investigator based on reported adverse events.

9.7 Vital Signs

Vital signs, including measurement of systolic and diastolic blood pressure, pulse, heart rate are to be measured.

9.8 Electrocardiogram

An ECG will be completed during the screening period to assess for cardiac conduction abnormalities.

9.9 Concurrent Medications

All prescription and non-prescription medications including pharmacologic doses of vitamins, herbal medicines, or other non-traditional medicines, taken from 4 weeks prior to the first dose of amitriptyline through the last study visit must be documented and recorded in the CRF.

9.9.1 Prohibited Concurrent Medications

The following medications are prohibited during the study:

- Antidepressants, including monoamine oxidase inhibitors, selective serotonin reuptake inhibitors, and tricyclic antidepressant other than the study drug.
- 9.9.2 Prohibited Procedure/Device
 - Anticipation of changing CGM device or modifying CGM settings should be discussed with the study team to determine whether these changes will potentially interfere with the study.

9.10 Efficacy Measurements

On all Treatment visit days, dosing will occur after all safety and efficacy assessments scheduled for that visit are complete.

9.10.1 Primary Objective Assessment

The primary objective assessment will be done through the determining areaunder-curve for CGM glucose level < 70/54 mg/dL and the total and recognized hypoglycemic episodes based on CGM data and hypoglycemic event reports, respectively.

A single CGM hypoglycemic episode will be defined by any CGM readings < 70 mg/dL lasting equal to or more than 20 minutes on the CGM data.

A participant will complete a hypoglycemic event report for all hypoglycemic events during the surveillance periods. A hypoglycemic event report will include information about whether the participants perceive symptom(s) for hypoglycemic episodes recorded based on CGM.

At each visits, CGM data will be downloaded into a secure system and exported into an Excel format, and the hypoglycemic event reports will be prepared for analysis.

9.10.2 Secondary Objective Assessment

In brief, the count of severe hypoglycemic episodes will be generated by participant surveillance at each Visit/telephone call. The hypoglycemic/nocturnal hypoglycemic courses, and other glucose regulation will be assessed with CGM data download and venous blood HbA1c assessment. A nocturnal hypoglycemia will be defined for all hypoglycemic episodes occur during 00:00-06:00 on CGM clock. Hypoglycemia awareness status and fear of hypoglycemia status will be assessed through hypoglycemia awareness questionnaires (Gold, Clark and Pedersen-Bjergaard) and Hypoglycemia Fear Survey Questionnaire. CGM data will be collected at Visit 1-4, and the questionnaires will be completed by study subjects at the first, second and the last Visit, and with the follow-up phone calls.

9.11 Safety Measurements

This study will utilize the CTCAE (NCI Common Terminology Criteria for Adverse Events) version 4.0 for AE and SAE reporting. An electronic copy of the CTCAE v.4 can be found at: https://evs.nci.nih.gov/ftp1/CTCAE/CTCAE_4.03_2010-06-14_QuickReference_5x7.pdf

9.11.1 Adverse Events

An adverse event is the appearance or worsening of any undesirable sign, symptom, or medical condition occurring after starting the study drug even if the event is not considered to be related to study drug. For the purposes of this study, the terms toxicity and adverse event are used interchangeably. Medical conditions/diseases present before starting study drug are only considered adverse events if they worsen after starting study drug. Abnormal laboratory values or test results constitute adverse events only if they induce clinical signs or symptoms, are considered clinically significant, or require therapy

Collection of adverse events will begin following the initial treatment with amitriptyline and continue through the last follow-up visit. Adverse events will be documented in the study source record and recorded in the CRF.

Information about all adverse events, whether volunteered by the subject, discovered by investigator questioning, or detected through physical examination, laboratory test or other means, will be collected and recorded and followed as appropriate.

The occurrence of adverse events should be sought by non-directive questioning of the patient at each visit or phone contact during the study. Adverse events also may be detected when they are volunteered by the patient during or between visits or through physical examination, laboratory test, or other assessments. As far as possible, each adverse event should be evaluated to determine:

- 1. The severity grade based on CTCAE v.4
- 2. The relationship of the event to the study drug(s): definite, probable, possible, unlikely, not related. [For multi-drug regimens, relationship will be assessed for each drug].
- 3. The duration: start and end dates, or continuing at final follow-up visit
- 4. Action taken: (e.g. study drug interrupted or dosage modified, concomitant medication taken, non-drug therapy, hospitalization, or no action taken)
- 5. Whether the event constitutes a Serious Adverse Event (SAE)

All adverse events will be treated appropriately. Such treatment may include changes in study drug treatment as listed in the dose modification section of this protocol (see section 7 for guidance). Once an adverse event is detected, it should be followed until its resolution, and assessment should be made at each visit (or more frequently, if necessary) of any changes in severity, the suspected relationship to the study drug, the interventions required to treat it, and the outcome.

9.11.2 Serious Adverse Events

Information about all serious adverse events will be documented in the study source record and recorded in the CRF. A serious adverse event is an undesirable sign, symptom or medical condition which:

- Is fatal or life-threatening
- Results in persistent or significant disability or incapacity
- Requires inpatient hospitalization or prolongation of existing hospitalization (unless the hospitalization is for routine treatment or

monitoring of the studied indication, or elective or pre-planned treatment of a pre-existing condition unrelated to the indication under study)

- Causes a congenital anomaly or birth defect
- Is medically significant, i.e., defined as an event that jeopardizes the subject or may require medical or surgical intervention to prevent one of the outcomes listed above

Toxicities which fall within the definitions listed above must be documented as an SAE regardless if they are felt to be treatment related or not.

9.11.3 Serious Adverse Event Reporting Requirements

An event determined to be an SAE must be reported to the IRB and the FDA according to the requirements described below:

IRB Notification:

The PI is responsible to report SAEs that meet the definition of an Unanticipated Problem through the ERICA system within 10 working days from the time the investigator learns of the event. An Unanticipated Problem is an event that is:

- Unexpected unforeseen by the investigator in terms of nature, severity, or frequency, given the research procedures and the subject population being studied
- **Related or Probably Related** determined by the investigator to be related or probably related to participation in the clinical trial
- **Greater Risk** the severity or scope of the event suggests that the research places subjects or others at greater risk of harm than was previously known or recognized

FDA Notification:

FDA regulations require the PI to report any serious and unexpected adverse event for which there is a reasonable possibility that the drug caused the event. Fatal or life-threatening events that meet these criteria must be reported within 7 calendar days from the time the investigator learns of the event. All other reportable events must be reported within 15 calendar days. The SAE should be reported on a MedWatch form and submitted as an amendment to the IND. For studies without an IND, the MedWatch report should be submitted to the FDA through the voluntary reporting method.

9.11.4 Reporting of Pregnancy

Although pregnancy is not considered an adverse event, it is the responsibility of the PI or their designee to report any pregnancy or lactation in a subject, including the pregnancy of a male subjects' female partner as an SAE. Pregnancies or lactation that occurs during the course of the trial or within 30 days of completing the trial or starting another new therapy, whichever is earlier, must be reported to the IRB, FDA, and the funding sponsor as applicable. All subjects and female partners who become pregnant must be followed to the completion/termination of the pregnancy. Pregnancy outcomes of spontaneous abortion, missed abortion, fetal death, intrauterine death, miscarriage and stillbirth must be reported as serious events.

9.12 Study Protocol Modification or Study Termination

The study protocol will be modified if:

• If the adherence/recruitment is below expectation or not meet grant timelines

The study protocol will be stopped if:

- The funding is exhausted, or
- The risk to benefit ratio is higher than expected

10 STATISTICAL CONSIDERATIONS

The statistical analyses of the pilot study will evaluate feasibility and address questions concerning trial conduct and outcomes, as well as power analysis for sample size which must be resolved in order to develop a rigorous design for the full scale trial of the final study. These analyses will be primarily descriptive.

The statistical analyses to evaluate the effects of the intervention on the primary and secondary outcomes will be conducted in both the pilot and final studies. For the pilot study, we will apply the exact Wilcoxon rank sums test as adapted to compare the primary outcome defined by the ratio of recognized-to-total (i.e. CGM) hypoglycemic events between the amitriptyline and placebo treatments under the assumption of no-carry over effects. Hodges-Lehman estimates and associated exact 95% confidence intervals will provide estimates of the size of the treatment effect. Other outcomes will be analyzed using either a similar nonparametric approach or mixed effect models parameterized to estimate the effects of treatment and period.

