| MedDRA | Medical Dictionary for Regulatory Activities |
| MTD | Maximum Tolerated Dose |
| NIH | National Institutes of Health |
| NIDDK | National Institute of Diabetes and Digestive and Kidney Diseases |
| PI | Principal Investigator |
| rtCGM | Real-time continuous glucose monitoring |
| SAE | Serious Adverse Event |

STATEMENT OF COMPLIANCE

I confirm that I have read this protocol, and I will conduct the study as outlined herein and according to the ethical principles stated in the latest version of the Declaration of Helsinki, the U.S. code of federal regulations (CFR) applicable to clinical studies (45 CFR Part 46, 21 CFR Part 50, 21 CFR Part 56, 21 CFR Part 312 and/or 21 CFR Part 812), and the applicable ICH guidelines for Good Clinical Practice (GCP).

I will promptly submit the protocol to the IRB for review and approval. Once the protocol has been approved by the IRB, I understand that any modifications made during the course of the study must first be approved by the IRB prior to implementation except when such modification is made to remove an immediate hazard to the subject.

I will provide copies of the protocol and all pertinent information to all individuals responsible to me who assist in the conduct of this study. I will discuss this material with them to ensure that they are fully informed regarding the study treatment, the conduct of the study, and the obligations of confidentiality.

Note: This document is signed electronically through submission and approval by the Principal Investigator in the University of Utah IRB Electronic Research Integrity and Compliance Administration (ERICA) system.

STUDY SUMMARY

| Title | The Use of Amitriptyline for Improving Hypoglycemia Recognition and Course | | | |
|---------------------------|--|--|--|--|
| Short Title | Amitriptyline as an anti-hypoglycemic agent | | | |
| Protocol Number | IRB # 00110853 | | | |
| IND | Pending – applying for IND exemption | | | |
| Phase | Pilot, clinical phase II | | | |
| Design | Double blind, randomized, placebo control, cross- over design | | | |
| Study Duration | 38 weeks | | | |
| Study Center(s) | University of Utah Hospital and Clinics | | | |
| Objectives | To evaluate whether amitriptyline improves the hypoglycemia course and the ability to recognize hypoglycemia in type 1 diabetes patients who are using real-time continuous glucose monitoring devices | | | |

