4 STUDY DESIGN

4.1 Description

The current investigation is a pilot phase II clinical trial with placebo control, randomization and double-blinding design.

After the initial recruitment (Visit 1), the study participants will enter a two-week "Runin Period", during which the participants will be asked to continue their CGM use and record their symptom(s) on Hypoglycemic Event Reports for all their hypoglycemic events. For the participants who meet the criteria to be initiated on study drug (see recruitment criteria), they will then be randomized to be initiated either on daily amitriptyline or a matching placebo (Visit 2). All participants will undergo a two-week drug "Titration Period", and at the end of this period (i.e., the end of Week 4), the amitriptyline dose will be titrated up with a matching placebo and continued until Visit 4. During this "Intervention Period", the patient will receive telephone follow-ups at Week 5 and Week 7, and undergo a return visit (Visit 3). After Visit 3, the participants will again start to record their hypoglycemic symptoms, and then return to Visit 4 at the end of the Intervention Period. The participants will then undergo a two-week study drug "Tapering Period" to complete the study drug intervention. At week 27 and 39 of the study, the participants will be assessed with follow-up questionnaires.

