4.2 Number of Subjects

Up to 80 participants are expected to be enrolled into the study for the Run-in Period assessment. For the study drug testing phase, 24 participants will be randomized and equally divided into two arms (i.e., 12 participants in the amitriptyline arm and 12 participants in the matching placebo arm).

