5.2 Exclusion Criteria

Yes/No (a response of "Yes" indicates the subject is ineligible)

- 1. _____ Ongoing or recent history of major depressive disorder, or other ongoing major psychiatric disorders
- 2. _____ History of anti-depressant use within the last three months
- 3. _____ Insulin pump linked to a CGM with programmed automatic insulin adjustment/suspension

- 4. _____ History of advanced cardiac, liver, kidney and neurological disease
- 5. _____ Active malignant
- 6. _____ Uncontrolled HIV diseases
- 7. _____ Advanced diabetic retinopathy, neuropathy or nephropathy
- 8. _____ Frequent acetaminophen use which can disrupt CGM accuracy
- 9. _____ Pregnancy or female of child-bearing potential unable to practice effective contraception during the study period
- 10. _____ Breastfeeding female or female with prospective plan to initiate breastfeeding
- 11. _____ Ongoing history of alcohol abuse
- 12. _____Contraindication to amitriptyline use, including hypersensitivity to amitriptyline or any component of the formulation, coadministration with or within 14 days of MAOIs and coadministration with cisapride
- 13. _____ Inability to understand or cooperate with study procedure, including taking study drugs and record hypoglycemic symptoms

The participants meeting the above criteria will enter "Run-in Period". At the Visit 2, the following additional exclusion criteria will be applied before study drug randomization:

- 14. _____ < 80% of CGM readings available over the last 2-week period
- 15. _____ Time spent in hypoglycemia (i.e., < 70 mg/dL) for < 5% over a 2week period on based on CGM reading.

I verify that this subject meets all eligibility criteria for enrollment onto this study

Investigator Signature

Date

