8 STUDY CALENDAR

| Period | Screening ¹ /Run-in | | Т | Follow-up | | | | |
|---|-----------------------------------|------------------|----|-----------|----------------|----------------|----|----|
| Visit No. | 1 | 2 | _2 | _2 | 3 | 4 | _3 | _3 |
| Week ⁴ | -4 to 1 | 3 | 5 | 7 | 11 | 13 | 27 | 39 |
| Assessments | | | | | | | | |
| Informed consent | Х | | | | | | | |
| Inclusion/Exclusion criteria | Х | | | | | | | |
| Demographics | Х | | | | | | | |
| Vital signs | Х | Х | | | Х | Х | | |
| Physical Examination | Х | X ⁵ | | | X ⁵ | X ⁵ | | |
| Pregnancy Test | Х | Х | | | | | | |
| ECG | | \mathbf{X}^{1} | | | | | | |
| Comprehensive Metabolic Panel ⁶ | Х | | | | | | | |
| HbA1c | | Х | | | | Х | | |
| AE Assessment | | Х | Х | Х | Х | Х | | |
| Concomitant Medications | Х | Х | | | Х | Х | | |
| Investigational Drug Treatment | | Х | Х | Х | X | X | | |
| Primary Objective Assessment | X ⁷ | X | | | X | X | | |
| Secondary Objective Assessment | X ⁷ | Х | | | X | X | X | X |

- 1. All screening procedures should be completed within 4 weeks of study enrollment, except that an ECG and laboratory evaluation completed within 3 months will be considered as valid.
- 2. Telephone call follow-up to assess participants' adverse events, and to remind study drug titration/adherence.
- 3. Telephone call follow-up to assess participants' general well-being, and to complete questionnaire surveys for Secondary Objective Assessment.
- 4. All visits/telephone calls can occur within +/- 3 days of the anticipated dates based on the schedule calendar
- 5. Follow-up physical exam to be conducted at the discretion of PI/Sub-investigator based on reported adverse events.
- 6. Comprehensive Metabolic penal include Albumin, Alkaline Phosphatase, Aspartate Aminotransferase, Alanine Aminotransferase, Total Bilirubin, Calcium, Carbon Dioxide, Creatinine, Chloride, Glucose, Potassium, Protein, Sodium and Urea Nitrogen.
- 7. Including instructions about Hypoglycemic Event Reports and conducting questionnaires surveys to assess baseline status. Will only be provided only after obtaining the consent.

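### Section 10 makes no stated use of the run-in recognised-to-total ratio, and its cross-over wording does not fit the two parallel arms; the unadjusted comparison is valid but can be less precise

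*Combined protocol and SAP*

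**What the plan says.** Section 10 states that for the pilot "we will apply the exact Wilcoxon rank sums test as adapted to compare the primary outcome", which is the recognised-to-total ratio. Hodges-Lehmann estimates with exact 95% intervals give the size of the effect. The adaptation of the test is not defined. The section does not mention run-in, baseline, change or covariates for this outcome, and it does not say which recording window forms the ratio. It assumes no carry-over. Other outcomes get a similar nonparametric method or mixed models with treatment and period terms. ANCOVA appears in the list of abbreviations but not in Section 10.

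On design, the Study Summary says "Double blind, randomized, placebo control, cross- over design". Section 4.2 says "24 participants will be randomized and equally divided into two arms", and Sections 4.1 and 6.1 give each arm one treatment with no switch.

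On data, Section 4.1 says that in the run-in "participants will be asked to continue their CGM use and record their symptom(s) on Hypoglycemic Event Reports", and later that "After Visit 3, the participants will again start to record their hypoglycemic symptoms", up to Visit 4. The Study Calendar puts Visits 3 and 4 at weeks 11 and 13. It schedules a primary objective assessment at Visit 2, and its note to the Visit 1 assessment reads "Including instructions about Hypoglycemic Event Reports and conducting questionnaires surveys to assess baseline status". Section 9.10 adds that on treatment visit days "dosing will occur after all safety and efficacy assessments scheduled for that visit are complete".

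**The concern.** The trial plans to record the same ratio over two weeks before randomisation and over two weeks at the end of treatment, yet the analysis does not say what the first recording is for. Three analyses remain open: follow-up values by arm, change from run-in by arm, or a within-person cross-over contrast. They estimate the effect with different precision, and the choice could be made after the data are seen.

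Two things are at stake. With 12 per arm, a baseline measure of the outcome is one of the few sources of extra precision that costs no new data. Section 10 also makes the power analysis for the full trial a purpose of the pilot. The run-in to follow-up correlation is a direct input to that analysis, and no plan to report it is given.

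**Working it through.** **No figure to reproduce.** The plan gives no power calculation, effect size, standard deviation or baseline correlation. The only checkable number is 24/2 = 12 per arm, which agrees with Section 4.2.

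**Is a baseline ratio available?** Yes. Event reports and CGM cover the run-in (Sections 4.1 and 9.10.1), and the Visit 2 assessment precedes dosing. Randomisation already depends on run-in CGM data: criterion 15 in Section 5.2 excludes "Time spent in hypoglycemia (i.e., < 70 mg/dL) for < 5" percent of a two-week period.

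**Is the unadjusted test valid?** Yes. The exact two-sided test at 12 v 12 rejects at U ≤ 37 or U ≥ 107, with size 0.0449 (two-sided 5% is assumed from the 95% interval). In simulation (40,000 trials per setting, normal data, r from 0 to 0.7) its Type I error was 0.043 to 0.045.

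**Variance of the mean difference, parallel arms, N = 24**

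- Adjusted relative to unadjusted, one normal covariate: (1 − r²)(N − 3)/(N − 4) = (1 − r²)(21/20) = 1.05(1 − r²).
- Change score relative to unadjusted: 2(1 − r).

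| Assumed r | 1.05(1 − r²) | Change | 2(1 − r) | Change |
|---|---|---|---|---|
| 0 | 1.050 | +5% | 2.0 | +100% |
| 0.3 | 1.05 × 0.91 = 0.956 | −4% | 1.4 | +40% |
| 0.5 | 1.05 × 0.75 = 0.788 | −21% | 1.0 | 0% |
| 0.7 | 1.05 × 0.51 = 0.536 | −46% | 0.6 | −40% |

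- Break-even for adjustment: 1.05(1 − r²) = 1, so r = √(1/21) = 0.218. If the lost degree of freedom is also counted in the interval width (t on 21 rather than 22 df), it is 0.230. On variance it is 0.229 with 22 analysed and 0.243 with 20.
- Change score against adjustment: 2(1 − r) = 1.05(1 − r)(1 + r) gives 2 = 1.05(1 + r), so r = 0.905. Below that, adjustment has the smaller variance.

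**Rank-based version.** Power of the exact Wilcoxon test against the same test on pooled baseline-adjusted residuals, at an assumed difference of 1.144 SD:

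| Assumed r | Unadjusted | Adjusted residuals |
|---|---|---|
| 0 | 0.725 | 0.699 |
| 0.22 | 0.726 | 0.719 |
| 0.3 | 0.721 | 0.737 |
| 0.5 | 0.722 | 0.816 |
| 0.7 | 0.727 | 0.931 |

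At an assumed 1 SD, the rank-sum test gave 0.60 to 0.61, and rank-based ANCOVA gave 0.58, 0.61, 0.68 and 0.81 at r = 0, 0.3, 0.5 and 0.7. The direction is the same as for the mean difference, with about no gain at r of about 0.3 or below. Type I error of the residual test was 0.044 to 0.046.

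**The case against.** The strongest reply is that nothing here is wrong. Randomisation makes the unadjusted comparison valid, an exact test with few assumptions is defensible at 12 per arm, and Section 10 calls pilot analyses primarily descriptive. The first two points stand and limit this to a matter of efficiency and prespecification. The third stands only in part: the descriptive remark closes the feasibility paragraph, and the next paragraph commits to treatment comparisons in both the pilot and the final study.

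A second reply is that the carry-over and period wording points to a cross-over analysis, in which case the figures above are irrelevant. That stands as a limit on the figures. It does not rescue the text, because Sections 4 and 6 describe no second treatment period.

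A reader might infer three stronger things that the documents do not support:

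- That the result would be biased without adjustment. It would not.
- That the planned exact Hodges-Lehmann interval would shrink by the percentages above. Those are normal-theory figures for a mean difference, whereas the ratio is bounded and rests on a limited number of episodes.
- That the likely gain is known. Under assumed means of 8 to 25 episodes per window and assumed person-level correlations of 0.3 to 1.0, simulated r ran from about 0.17 to 0.83, or +2% to −67% in variance. The documents do not narrow this range.

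**Conclusion.** The point holds as one of precision and prespecification, not validity. Section 10 gives the run-in ratio no role, leaves the adaptation of its test undefined, and uses cross-over terms for what the design sections describe as two parallel arms.

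If the arms are parallel and all 24 are analysed, linear adjustment costs about 5% in variance when run-in is uninformative, breaks even at r of about 0.22 (0.23 on interval width), and saves 21% at r = 0.5 and 46% at r = 0.7. All values of r are assumptions. A simple change score is the poorer way to use run-in unless r exceeds about 0.90. For AUC below 70 and 54 mg/dL the role of run-in is equally unstated. The gain there is not quantified, and it may be smaller because criterion 15 truncates baseline time below 70.

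**What to change.** 1. Reconcile the cross-over, carry-over and period wording in the Study Summary and Section 10 with the parallel arms in Sections 4 and 6, and define how the Wilcoxon test is adapted. If a cross-over is meant, the steps below need rethinking.
2. Prespecify as the leading analysis the Visit 3 to Visit 4 ratio compared by arm, with the run-in ratio as covariate, giving an adjusted estimate and 95% interval. Name one method in advance: ANCOVA, or a rank test on baseline-adjusted residuals to stay close to the planned exact method. Keep the unadjusted exact Wilcoxon and Hodges-Lehmann result as supportive. When fixing the window, also reconcile Section 6.2.3, which ties the end of the intervention to Visit 3, with Section 4.1, which ties it to Visit 4.
3. Do not use a simple change score.
4. Include the run-in value in the same way for AUC below 70 and below 54 mg/dL.
5. Report the observed run-in to follow-up correlation for sizing the full trial.

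Cost: a few sentences in Section 10, one degree of freedom and no new data. The downside is about 5% more variance if run-in proves uninformative, and about no gain from the rank version at r of about 0.3 or below.
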